The proposed 6-mo. pilot trial will compare the feasibility and effectiveness of DPP delivered through Facebook (DPP-FB) or group format delivered remotely by phone conference call (DPP-R) in 30 adults (age ≥ 18 yrs.) with prediabetes. Both interventions will be delivered through the CES, which serves as the community outreach arm of all land grant universities through over 2,900 offices across the U.S. The Kansas State Research and Extension (KSRE) (Kansas version of CES), is well positioned, but underutilized for the delivery of DPP in rural areas. Delivery of DPP by a well-recognized entity, such as the KSRE, may improve the probability of dissemination and long-term program sustainability. Two CES offices serving rural counties in Kansas will be randomized (1:1) to the DPP-FB or DPP-R arms. Our research team will train 2 professional staff from KSRE (with backgrounds in nutrition programming and family consumer science) who will deliver the DPP intervention. Outcomes will include body weight

and moderate-vigorous physical activity assessed at baseline, 3 mos. and 6 mos., participant retention, i.e. weight assessed at 6 mos., program attendance (percentage of 16 sessions attended), and the fidelity of intervention delivery. i.e., the delivery of $\geq 80\%$ of scheduled content as determined by reviewing audio recordings of all DPP sessions. This project will address the following aims:

Primary aim: **Compare weight and MVPA between DPP-FB and DPP-R across 6 mos.** We expect greater weight loss and MVPA in the DPP-R arm compared with the DPP-FB arm.

Secondary aim: **Compare the feasibility of DPP-FB and DPP-R across 6 mos. based on participant retention and program attendance.** We expect greater participant retention and program attendance in the DPP-R arm compared with the DPP-FB arm.

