Does the candidate have a brother or sister with diabetes?	 - 1	 - 0
Does the candidate weigh as much as or more than the weight listed for their height?	 - 5	 - 0
Is the candidate younger than 65 years of age and gets little or no activity in a typical day?	 - 5	 - 0
Is the candidate between 45 and 64 years of age?	 - 5	 - 0
Is the candidate 65 years of age or older?	 - 9	 - 0
Total Risk Score (score must be 9 or greater to qualify for enrollment in 'At-Risk' category):		

Participants/Recruitment: Men and women (n=15 per arm) who satisfy the inclusion/exclusion will be recruited through local physician's offices, social media, KSRE offices, marketing/listservs, and local businesses. Interested potential participants will fill out an initial eligibility questionnaire via website or over the phone with a study team member. If they pass the screening, a consent session will be scheduled over the phone or over Zoom. The consent form will be emailed to participants prior to the consent session so ensure understanding of the study. The participant will have the option to sign the consent form and email it to the study coordinator or sign the consent form in REDCap.

Inclusion/exclusion criteria. *Inclusion:* 1) Prediabetes as defined as A1C = 5.7-6.4%, fasting glucose = 100-125 mg/dl, (confirmed from physician/medical record in the previous year), history of gestation diabetes mellitus OR a positive result based on the CDC- DPP screener (see figure), 2) Age ≥ 18 yrs., 3) Willing to commit to participate on a weekly basis for the 6 month intervention, 4) Living in the county of a rural KSRE local unit. Rural counties will be defined using the American Community Survey definition which categorizes a county as rural if the population is $< 65,000$ (23), 5) Internet access and capability to use Zoom, 6) Clearance from primary care physician and 7) Access to a scale. *Exclusion.* 1) Diagnosis of T2D, 2) Unable to participate in physical activity.

Randomization: Two rural KSRE local units will be randomized in a 1:1 ratio to either DPP-FB or DPP-R.

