DPP-FB intervention delivery. Formal meetings will not be scheduled. Logistics. Participants will be asked to join a *secret*, lifestyle coach moderated, Facebook® group. The content in a *secret* Facebook® groups is accessible only to invited members, and the existence of the page is hidden from the public. Participants with existing Facebook® accounts will be advised on adjusting privacy settings to control access by other members of their *secret* Facebook® group. Participants will access Facebook® with the iPad provided using Wi-Fi, thus participant's personal data plans will not be impacted. The lifestyle coach will post new modules of the Prevent T2 curriculum to Facebook® weekly over months 1-6 (modules 1-24) and monthly over months 7-12 (modules 25-30). New modules will be posted prior to 9 a.m. on Mondays. De-identified individual participant self-monitoring data (diet, PA, weight loss) and a brief comment from the lifestyle coach regarding the performance of the group will be posted on Tuesday a.m. This allows participants to assess their progress relative to others in the group. Brief discussion points such as "what strategies to increase your level of PA will you try this week?" will be posted on Wednesday and Friday AM. These posts are designed to reinforce the primary objectives of each module and to facilitate inter-participant discussion around these topics. Participants will be asked to comment on each of the discussion point posts. The lifestyle coach will monitor the responses to the discussion point posts daily and will answer questions and/or correct any misinformation that may be included in participant posts. The Friday morning post will include a reminder to sync self-monitoring devices by midnight on Sunday. New posts will be "pinned" to the top of the wall and included in the "announcements section", to ensure the new posts are easily identified. Participant engagement, which will be tracked across the 6-mo. trial, can take the form of "liking" or "commenting" on the posts, or contributing new posts. Lifestyle coaches will monitor the Facebook® group on the Monday following the posting of a new curriculum module to determine if the module has been accessed. This is analogous to attendance in the Zoom® group. Lifestyle coaches will send email reminders to participants who do not access 2 consecutive module postings. Participants will be encouraged to contact lifestyle coaches with any questions that arise during the intervention using Facebook® messenger, which automatically alerts lifestyle coaches that a message has been received.

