
No data is downloaded from Facebook and transferred to KUMC servers.

Self-monitoring. Participants will be asked to self-monitor weight, minutes of physical activity, steps (Fitbit provided), and fruit and vegetable intake each week. Participants in both intervention arms will be required to enter their data into REDCap, including weight (scale provided), diet and physical activity between weekly meetings. Self-report data will be used by lifestyle coaches to inform individual participant feedback.

Attendance at group meetings and self-reported weights will be recorded weekly.

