Selection and training Lifestyle Coaches: Part of the translational nature of the DPP is that the lifestyle coaches can be 'lay-persons' without advanced degrees in exercise physiology, behavioral psychology or health education. A primary lifestyle coach will be selected at the randomized KSRE offices in conjunction with our partners at KSRE ([name] and [name]). The study coordinator will be trained to ensure there is adequate coverage in the event of illness, job change, etc. The study coordinator will provide a 1-day on-site training at each KSRE local unit prior to initiating the intervention. DPP-R training. Prior to the intervention lifestyle coaches at the DPP-R site will attend, four 1-hr training sessions via video chat. Audio recordings of previous group remote delivery recordings from our NIH trial (DK108732) will be utilized to demonstrate effective leadership and facilitation techniques in a group call setting. The 4 training sessions will be used to reinforce strategies taught during on-site training. Prior to initiating the intervention all lifestyle coaches will be required to successfully conduct 3 simulated sessions over the phone with members of the research staff serving as participants. DPP-FB training. Lifestyle coaches at the DPP-FB site will also attend four 1-hr follow-up training sessions via video chat. Audio recordings of in-person group sessions from previous studies will be utilized. Prior to initiating the intervention, lifestyle coaches for the DPP-FB group will be required to successfully conduct 2 simulated discussions in a mock Facebook group conducted with CES or KUMC research staff as participants. These sessions will be observed and evaluated by the study coordinator either via FaceTime or Zoom. A standardized checklist, which includes the important skills/strategies taught during training, will be used to assure that lifestyle coaches for both intervention arms demonstrate mastery of these skills.

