Intervention fidelity: To assure quality control and standardization of intervention delivery all DPP-R sessions will be audio recorded and compared with a standardized checklist of content to be delivered. For the DPP-FB group, the private group will also be audited to ensure quality control and standardized intervention delivery. Our study coordinator will randomly review 1 session/mo. (total of 6 sessions for each intervention arm). Lifestyle coaches who fail to deliver at least 80% of the scheduled content will receive additional training with the study coordinator using video chat over Zoom. In the event the primary lifestyle coach is unable to lead a DPP session, the secondary lifestyle coach will be available as substitute or the study coordinator, thus assuring continuity of the intervention.

Incentives: Participants will be compensated \$20 for baseline, 3 mo. and 6 mo. outcome testing assessments.

OUTCOME ASSESSMENTS

All outcome assessments will be completed by KUMC research staff at the KSRE local unit at baseline, 3 mo. 6 mo. and 12 mo. KUMC research staff will follow all COVID procedures for testing that are outlined in the CPAWM COVID-19 Procedures- Off-Site attachment.

Anthropometrics measurements. Body weight will be assessed to the nearest 0.1 kg with a calibrated scale (Belfour Inc., Model #PS6600, Saukville, WI). All participants will be weighed between the hours of 6 and 11 am following a 12 hr. fast in a standard hospital gown. Standing height will be assessed to the nearest cm with a stadiometer (Model PE-WM-60-84, Perspective Enterprises, Portage, MI).

Physical activity. Physical activity will be assessed using an ActiGraph (wGT3x-BT) portable tri-axial accelerometer (ArchiMed Co, Lyon, Auvergne-Rhone-Alpes, France) which has been

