shown to provide valid and reliable assessments of PA in adults. Participants will wear the ActiGraph on a belt over the non-dominant hip at the anterior axillary line during waking hours for 7 consecutive days, except for bathing, swimming, and contact sports. A 7-day monitoring period provides a reliable estimate of moderate-to-vigorous PA. ActiGraph data, aggregated over 1-min epochs, will be processed using the protocol used for adults in the 2003-2004 and 2005-2006 cycles of NHANES using the following intensity cut-points: sedentary (< 1.0 METs \leq 100 counts/min), light (METs 1.1-2.99; 101-2019 counts/min.), moderate (METs 3.0-5.99; 2020-5998 counts/min) and vigorous (\geq 6 METs; \geq 5999 counts/min). ActiGraphs will be given to participants during outcomes testing with a prepaid envelope to mail back to the investigators after wearing for 7 days. Participant retention/program attendance. Lifestyle coaches in both intervention arms will maintain records of participant retention and program attendance. Retention will be defined as attendance at 6 mo. and 12 mo. outcome testing. Program attendance will be defined as being present as the beginning and end of the class/call and reporting weekly data.

End study survey. At the end of the 6 mo. intervention, a survey will be conducted to ask about your experience with the program.

Focus group. At the end of the 6 mo. intervention, a recorded focus group will be conducted in all participants to gather information on the overall ease and enjoyment of the program. Questions on barriers to healthy eating and physical activity, time commitment, recommending the program to friends/family,

Statistical analysis & Data management: Baseline measures and demographic characteristics will be summarized for the complete sample using means and standard deviations for continuous variables and frequencies and percentages for categorical variables. Weight loss will be calculated as the difference in body weight between baseline and 6 months. All analyses will be conducted using SAS 9.4 (SAS Institute, Cary, NC). We will compare change in body weight and MVPA between groups at 6 mos. and 12 mos. by using a two-sample t-test. Feasibility will be calculated as the percentage of participants who attended $>$ 75% of the scheduled sessions. We will also conduct a qualitative analysis of focus group and end study surveys to gain insight on the acceptability and enjoyment of the program and suggestions for improvement.

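### Presence in the attendance outcome is scored by each arm's own lifestyle coach with no planned check, so recording habits cannot be separated from delivery format

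*Combined protocol and SAP*

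**What the plan says.** The secondary aim in Specific aims is to "Compare the feasibility of DPP-FB and DPP-R across 6 mos. based on participant retention and program attendance".

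Under Outcome assessments (Participant retention/program attendance), "Lifestyle coaches in both intervention arms will maintain records of participant retention and program attendance". A session counts as attended if the participant is there at the start and the end and has also reported the weekly data. Under Statistical analysis & Data management, feasibility is the percentage of participants who attended more than 75% of scheduled sessions.

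Under Randomization, "Two rural KSRE local units will be randomized in a 1:1 ratio to either DPP-FB or DPP-R", which gives one office per arm. Under Selection and training Lifestyle Coaches, "A primary lifestyle coach will be selected at the randomized KSRE offices".

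In the Facebook arm, the coach looks at the group on the Monday after the "posting of a new curriculum module to determine if the module has been accessed", and the plan treats this as the counterpart of attendance in the Zoom group. That section ends: "No data is downloaded from Facebook and transferred to KUMC servers".

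Self-monitoring has participants in both arms enter their weekly data in REDCap. Intervention fidelity provides audio recording of DPP-R sessions, an audit of the Facebook group and a coordinator review of one session a month per arm, all directed at the content delivered. Online Safety describes monitoring of use of the Facebook page, to keep content appropriate.

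**The concern.** The person who scores presence in each arm is unmasked, is responsible for delivering the format being scored, and is in practice the only recorder in that arm. In DPP-R the coach has to note who is there at both ends of a 60-minute meeting of 12-15 people, some joining by phone, while leading it. In DPP-FB the coach reads module access from the page. No second record, duplicate scoring or check of attendance is described.

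Recorder and arm therefore almost coincide, and no analysis of the resulting data can tell a strict or lenient recorder from a better or worse attended format. The 75% cut adds to this, because a small change in credited sessions moves participants across it. The pilot is meant to supply data for an application for a larger trial, so a distorted attendance comparison would carry forward.

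**Working it through.** The plan gives no expected attendance, recording error rate or power figure, so there is no stated result to reproduce. The check has two parts.

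**1. Is attendance checked anywhere?**

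| Safeguard in the plan | What it covers | Attendance? |
|---|---|---|
| Audio recording of DPP-R sessions, audit of the Facebook group, monthly coordinator review (Intervention fidelity) | delivery of at least 80% of scheduled content | not stated |
| Monitoring of the Facebook page (Online Safety) | appropriate content | not stated |
| Research staff: "All outcome assessments will be completed by KUMC research staff at the KSRE local unit" (Outcome assessments) | testing visits at baseline, 3, 6 and 12 months | no; session attendance is given to the coaches |
| Participants' REDCap entries (Self-monitoring) | the weekly-data condition | yes, but not presence or module access |

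The last row matters. A coach cannot turn an absence into an attended session unless the participant has also entered data for that week. Failing to credit a session that was attended has no such brake.

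**2. How much could a recording difference matter?**

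From the plan: 24 core sessions in 6 months (Intervention overview), a cut above 75%, and 15 participants per arm. More than 75% of 24 is more than 18, so at least 19.

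Assumed: true attendance averages 75% in both arms; participants' own probabilities p vary as a beta distribution with SD 0.15; sessions are independent given p; one coach records exactly and the other does not.

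- Beta parameters: a + b = 0.75 × 0.25 / 0.15² − 1 = 7.333, so a = 5.5 and b = 1.833.
- Lenient coach, crediting a fraction f of absences: q = p + (1 − p)f. The mean shift is 0.25f, so 3 points needs f = 0.12 and 5 points needs f = 0.20.
- If only half of those absences have REDCap data, f falls to 0.06 and 0.10.
- Strict coach, missing a fraction k of attended sessions: q = p(1 − k). With k = 0.05 the mean shift is −0.75 × 0.05 = −3.75 points.
- Share passing: the average over p of P(Binomial(S, q) ≥ r), with S = 24 and r = 19, or S = 16 and r = 13.

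| Recording in one arm | 24 sessions (≥19) | 16 sessions (≥13) |
|---|---|---|
| Exact | 51% | 50% |
| Lenient, f = 0.12 / 0.20, all with REDCap data | 58% / 63% | 56% / 61% |
| Lenient, half with REDCap data (f = 0.06 / 0.10) | 55% / 57% | 53% / 55% |
| Strict, k = 0.05 | 42% | 40% |

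The second column is there because Specific aims defines attendance over 16 sessions. The choice of denominator hardly changes the result.

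On the 24-session scale the lenient shifts run from 54.6 − 51.4 = 3.2 points to 63.1 − 51.4 = 11.7 points. Multiplied by 15, that is about 0.5 to 1.8 participants. The sampling standard error of a difference between two arms of 15 is √(2 × 0.51 × 0.49 / 15) = 0.18, or 18 points.

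**The case against.** Several points on the other side stand.

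- **Attendance is not wholly in the coach's hands.** A reader might infer that it is, but the REDCap condition is participant-entered, so the concern is confined to presence and module access. A secondary coach or the coordinator may also stand in, so recorder and arm are nearly, not perfectly, the same.
- **The Facebook reading is not uncheckable.** A reader might infer this from the statement that no Facebook data are downloaded. That statement rules out an exported log held by the research team; it does not rule out looking at the page, which the audit and the page monitoring already involve. What is missing is a planned check of attendance.
- **Retention is not affected.** The coaches are told to record it, but it is defined by attendance at testing visits that research staff conduct, so it can be verified.
- **Larger figures are not realistic.** If every participant had the same 75% probability, a 5-point shift would move the share above the cut from 42% to 66%. That needs identical participants and the crediting of 20% of absences, all with REDCap data.
- **The effect is small beside sampling error,** feasibility is reported as a percentage with no test specified, and nothing in the documents shows that the two coaches would differ.

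It is also fair that coach-kept attendance suits a programme delivered by lay coaches, and that better records leave the larger confounding of one office per arm untouched. None of this supplies an attendance check. Sampling error does not excuse a systematic error either, and this one can be reduced with tools already in the study.

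**Conclusion.** The concern holds for the presence and module-access part of program attendance. With one office and one primary coach per arm, an unmasked recorder and no planned attendance check, the study could not tell a difference in recording habits from a difference in format.

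Under the stated assumptions, lenient recording by 3 to 5 points would create an apparent difference of about 7 to 12 percentage points in the share above the cut, or about 3 to 6 points if half of the wrongly credited absences lack REDCap data. Missing 5% of attended sessions would create one of about 10 points the other way. The error rates, the 75% attendance and the SD are assumptions, not figures from the plan. The conclusion is that the design could not detect such a difference, not that one will occur. Retention is outside this conclusion.

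**What to change.** Amend the paragraph on participant retention and program attendance:

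1. In DPP-R, take presence from the Zoom join/leave report where the host account provides it (an assumption; the plan does not mention it). Keep the coach's list as back-up and for matching phone callers to names.
2. In both arms, determine the weekly-data condition from REDCap entry dates.
3. Take retention from the research team's own outcome-testing records.
4. In DPP-FB, have the coach enter module access by study ID in REDCap each week. This is manual entry, so nothing is downloaded from Facebook. Have the coordinator re-read access for the audited week within the existing monthly audit.
5. In both arms, compare the coach's record with the independent source for the audited sessions (6 per arm) and report agreement by arm.
6. Reconcile the 16 sessions in Specific aims with the 24 in Intervention overview, so that the 75% cut has one denominator.

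The cost is protocol wording, matching of phone callers and a few minutes a month. The sources would still differ by arm, an automatic log against a coach's entry, which is why agreement should be shown separately.

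The protocol should also state that these steps reduce recorder bias only. Site, coach and the different attendance events (presence on a call against a module accessed) remain confounded with format.

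### Weight and MVPA are compared by t-tests on change with no missing-data rule, although the protocol itself expects retention to differ by arm; the month-3 data enter no stated analysis

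*Combined protocol and SAP*

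**What the plan says.** The only between-arm analysis of the two primary outcomes is in Statistical analysis & Data management: "We will compare change in body weight and MVPA between groups at 6 mos. and 12 mos. by using a two-sample t-test". The same paragraph fixes the weight endpoint: "Weight loss will be calculated as the difference in body weight between baseline and 6 months". The document names no analysis population, imputation, likelihood model or sensitivity analysis.

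Retention is tied to the outcome itself. The Specific aims describe it as "participant retention, i.e. weight assessed at 6 mos". The Participant retention/program attendance paragraph says "Retention will be defined as attendance at 6 mo. and 12 mo. outcome testing". The secondary aim adds: "We expect greater participant retention and program attendance in the DPP-R arm compared with the DPP-FB arm".

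MVPA needs one step more than the visit: "ActiGraphs will be given to participants during outcomes testing with a prepaid envelope to mail back to the investigators".

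The primary aim is to "Compare weight and MVPA between DPP-FB and DPP-R across 6 mos". The Specific aims list body weight "and moderate-vigorous physical activity assessed at baseline, 3 mos. and 6 mos", and the Outcome Assessments section also schedules month 3. Under Self-monitoring, weekly self-reported weights are recorded; their stated use is coaching feedback.

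**The concern.** A change score needs a follow-up value, and the plan names no substitute when it is absent. As written, a participant who misses the 6-month visit drops out of the primary comparison. The plan does not say this outright; it is an inference, but no stated rule offers another reading.

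The secondary hypothesis is that this will happen more often in DPP-FB. If those who leave differ in weight change from those who stay, the two arms' means are shifted by different amounts, and so is their difference. MVPA has the same exposure, plus devices that are not mailed back.

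The two arms keep contact in different ways (weekly live meetings against no scheduled meetings), so any link between dropout and weight change need not be the same in both. The estimates are meant to support a funding application for a larger trial, so a bias that can be reduced with data already collected is worth reducing.

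**Working it through.** The plan gives no figure to reproduce here: no SD, effect size, alpha, power or dropout rate. What follows is an illustration resting on assumptions.

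1. **Inputs from the documents.** 15 per arm (Participants/Recruitment). An SD of 6-month loss is borrowed from the cited trial of on-site group DPP in 234 rural women (Background): SE 0.4 kg, so SD = 0.4 × √234 = 6.12 kg. Applying it to this trial is itself an assumption.

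2. **Assumed inputs.** Mean 6-month loss 8 kg in DPP-R and 6 kg in DPP-FB (true difference 2.0 kg). Correlation 0.8 between 3- and 6-month loss. Retention pairs (DPP-R v DPP-FB) 90% v 80%, 85% v 75%, 85% v 66% and 90% v 65%. Probability of attending month 6 = expit(a + s·z3), where z3 is the standardised 3-month loss within arm and a is set to give the stated retention. A positive s means that people who lose less leave; a negative s means that people who lose more leave.

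3. **Formula.** Mean among those who remain = true mean + dropout × (mean of stayers − mean of leavers). The bias in the difference is this product in DPP-R minus the product in DPP-FB.

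4. **Base case, 85% v 66%, s = 1 in both arms.** Stayers and leavers average 8.65 and 4.32 kg in DPP-R, 7.39 and 3.30 kg in DPP-FB. Bias = 0.15 × 4.33 − 0.34 × 4.09 = 0.65 − 1.39 = −0.74 kg, so the estimate is 2.00 − 0.74 = 1.26 kg.

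5. **Other links** (estimate in kg, true value 2.00):

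| s in DPP-R v DPP-FB | 90/80 | 85/75 | 85/66 | 90/65 |
|---|---|---|---|---|
| 0 v 0 | 2.00 | 2.00 | 2.00 | 2.00 |
| 1 v 1 | 1.60 | 1.61 | 1.26 | 1.01 |
| 0.5 v 1.5 | 1.13 | 1.00 | 0.56 | 0.40 |
| 1.5 v 0.5 | 2.13 | 2.27 | 2.07 | 1.78 |
| 1 v 0 | 2.44 | 2.65 | 2.65 | 2.44 |
| −1 v −1 | 2.40 | 2.39 | 2.74 | 2.99 |
| 0 v −1 | 2.85 | 3.04 | 3.39 | 3.43 |

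6. **Against sampling error.** With about 13 and 10 completers, SE = 6.12 × √(1/13 + 1/10) = 2.57 kg, or roughly 2.5 kg. The base-case bias is 0.74 / 2.5 ≈ 0.3 of that.

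7. **What month 3 adds.** A repeated-measures model (arm, visit, arm-by-visit, baseline, unstructured covariance; 1,500 simulated trials, simulation error 0.06 kg) gives, in the base case, 2.05 kg if every non-completer attends month 3, 1.71 kg if half do and 1.33 kg if none do. At 85/75 with s = 1.5 v 0.5 it gives 2.07, 2.24 and 2.27 kg. A simpler likelihood estimate without the baseline covariate, in the base case, cuts root-mean-square error from 2.60 to 2.39 kg (all attend) or from 2.62 to 2.49 kg (half), with no change if none do. If dropout follows the unseen 6-month loss instead, completers give 1.08 kg and the model 1.64 kg (all) or 1.47 kg (half).

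8. **Limits of the simulation.** It covered months 3 and 6 only and did not test Kenward-Roger degrees of freedom. The documents give no MVPA SD, so no size is offered for MVPA.

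**The case against.** **Materiality.** This is a 30-person pilot, the bias is small beside its sampling error, and each arm is one local unit, so arm is confounded with place whatever model is used. All of that stands. It limits the weight of the point but does not remove it, since the change needs no new data.

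**The unequal retention is only a directional hypothesis.** No rate is given, and at 15 per arm a higher retention could mean one person. With a 4 kg gap between stayers and leavers in both arms, one extra dropout shifts the difference by 4/15 = 0.27 kg. The Incentives paragraph also pays participants for the 3- and 6-month assessments, which may hold losses down. The retention gaps of 10 to 25 points used above are assumptions.

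**The primary aim.** A reader might infer that leaving month 3 out contradicts an aim worded as spanning 6 months. The documents do not support that. The secondary aim uses the same phrase for retention, a single end-point measure, so it can simply mean over the 6-month trial. The 6-month endpoint is clearly defined. Using month 3 is an improvement, not the repair of a contradiction.

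**The model may help little.** Near-full correction needs all non-completers at month 3 and dropout that depends only on observed values. The documents give no expected month-3 attendance. At 85/75 with s = 1.5 v 0.5 and half attending, the gain is almost nil (2.24 against 2.27 kg). This stands and should be stated with the fix.

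**Conclusion.** The point holds as a cheap improvement that should be made, not as a flaw that invalidates the trial. Three facts rest on the text: t-tests on change with no missing-data rule, retention defined by the outcome visit and expected to differ by arm, and month-3 data that enter no stated analysis. That only attenders count is an inference from those facts.

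The size rests wholly on assumptions. For a true 2.0 kg, the retention pairs and links tried give 0.40 to 3.43 kg. These are not bounds: other rates or stronger links would go further. In the equal-link base case the bias is about 0.3 of a standard error.

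A reader might infer that the t-test is bound to understate a DPP-R advantage, because retention is expected to be higher there. The documents do not support a direction. They tie weight loss to session attendance, not to attending the testing visit. The bias reverses if people who lose more are the ones who leave, can go either way if the link differs by arm, and is nil with no link. Nor can it be said that the proposed model removes the bias; it reduces it under conditions that the documents do not establish.

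**What to change.** In Statistical analysis & Data management:

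- Replace the t-tests with a repeated-measures likelihood model, fitted separately for weight and MVPA, by assigned arm, including everyone with at least one post-baseline value. Terms: arm, visit, arm-by-visit and baseline value. Use unstructured covariance (compound symmetry if it does not converge) and Kenward-Roger degrees of freedom. Make the 6-month arm contrast primary.
- Include the 12-month visit in the same model if it is carried out, so that the stated 12-month comparison keeps an analysis. Reconcile the Specific aims, which describe a 6-month trial, with the Design overview, Outcome Assessments, retention and analysis text, which run to 12 months.
- Report by arm how many participants have each visit's weight and MVPA.
- As a sensitivity analysis for weight, fill a missing 6-month clinic weight with the change from the person's first to last self-reported weight inside a prespecified window around month 6. Home-to-home change is needed because clinic weights are fasted and gowned. In the base case, if a random half of non-completers report, the estimate is 8.30 − 6.55 = 1.75 kg.
- Do not carry baseline forward. With no true difference (6 kg mean loss in both arms) and the base-case dropout, it creates a DPP-R advantage of 0.85 × 6.65 − 0.66 × 7.39 = 0.77 kg.

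Cost: SAP wording and a few lines of SAS; no new data. State the limits: the model assumes missing at random, corrects only as far as non-completers attend month 3 (partly if half do, not at all if none do), still excludes people with no post-baseline value, and does not address the single local unit per arm. People who leave may also stop entering home weights, and no comparable fill is stated for MVPA.
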